10.4 Primary Objective

To compare the frequency of radiographically significant osteonecrosis in patients receiving intensive compared to conventional antihypertensive therapy.

The primary endpoint is the number of major joints (hips and knees) with extensive epiphyseal osteonecrosis ($\geq 30\%$ affected surface^{12,13,17}) on MRI after approximately 9 months of chemotherapy (during reinduction 2). All randomized patients with appropriate imaging are considered evaluable and all analyses will be done according to intent-to-treat.

A chart review of 140 TOTXVI patients meeting the eligibility criteria of this study showed the following distribution of the number of affected joints in the low BP within-target group vs. the above-target group:

	Number of affected joints					Total
	0	1	2	3	4	
Above-target (proportion, n)	0.583, 70	0.083, 10	0.233, 28	0.017, 2	0.083, 10	120
Within-target (proportion, n)	0.80, 16	0.05, 1	0.10, 2	0.00, 0	0.05, 1	20

Clearly in each BP group the distribution is bi-modal with local modes at 0 and 2.

The primary analysis will consist of two parts. In the first part the distribution of the number of affected joints will be compared by the exact one-sided Chi-square test comparing the probability of having at least 1 affected joint. Let $P_0(k)$ and $P_1(k)$ be the probability of k affected joints among patients above- and within-target respectively ($k=0,1,2,3,4$). We have noted in the preliminary data that the BP of 14.6% of the eligible patients was within target without any treatment. Therefore, the distribution of the number of affected joints in the control group is anticipated to be $PC(k)=0.854*P_0(k)+0.146*P_1(k)$, and the distribution in the treatment group is anticipated to be $PT(k)=P_1(k)$, $k=0,1,2,3,4$. Applying the preliminary data displayed above to this model, we obtain the anticipated distribution in the control and treatment group as follows:

	Number of affected joints k	
	0	1+
Control	0.615	0.385
Treatment	0.8	0.2

With $n=80$ subjects per group, the one-sided test has the exact power of 78.7% to detect the above anticipated difference at the 5% significance level. The power is calculated using Cytel Studio II.

In the second part, the mean number of affected joints within the treatment and control group will be estimated by the sample mean and a 95% confidence interval based on the t statistic. Difference in the mean number of affected joints between the two groups will also be estimated by the point estimate of the difference of two sample means and the t -statistic based 95% confidence interval. We note that although the sample space is discrete, the relatively large sample size ($n=80/\text{group}$) renders valid t statistic-based confidence intervals.

Bootstrap will be applied to check if the sample mean behaves similarly to a normally distributed random variable, and bootstrap confidence intervals will be applied if the t -distribution approximation is questionable. Additionally, we will compare the two arms by the two-sided chi-square test for ordered columns.

Time frame: The analysis will begin within 6 months after the MRI assessments of the last randomized patient is completed.

Responsible investigators: [name], [name]

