Intensive Low End Target (mmHg)	110						
Intensive High End Target (mmHg)	120						

Patients will begin antihypertensive therapy to achieve the targeted blood pressure on Day 4 of Remission Induction on TOT17. Patients already receiving antihypertensive therapy prior to Day 4 should have their therapy adjusted according to the guidelines below.

During outpatient visits, blood pressures measured should be performed after the patient has been sitting at rest for at least 10 minutes and is not experiencing pain or anxiety.

During induction, blood pressure adjustments will be made for each patient based on the mean blood pressure over the preceding 4 days (minimum 2 measurements) unless indication for immediate change is met (listed below). Blood pressures obtained while a patient is sedated for procedures should not be included in the evaluated blood pressures when determining whether to adjust antihypertensive medications. Patients with mean blood pressures outside of the target range should have antihypertensive therapy adjusted in an attempt to reach the goal range. However, if prior changes to medication have been made within 7 days and blood pressures are both 1) closer to the target range than at the time of prior medication change and 2) within 10mmHg of the goal range following that change, further modifications can be delayed until a subsequent visit.

Immediate changes to antihypertensive therapy are indicated if:

- 1) systolic pressures are more than 15mmHg above the high end target,
- 2) patients are experiencing headache, vision changes, or neurologic symptoms attributable to hypertension,
- 3) the patient has experienced an episode of syncope,
- 4) the patient's systolic pressure is below 90, or
- 5) the patient is experiencing unacceptable toxicity from their current antihypertensive therapy.

Patients will continue antihypertensive therapy (as needed to achieve the targeted blood pressure range) during phases of therapy with scheduled glucocorticoids (i.e. Induction and Continuation, including Reinduction 1 & 2). Patients should continue antihypertensive therapy during other phases if tolerated. Caution is warranted in consolidation (due to the risk of altered renal perfusion or kidney injury) and during immunotherapy (due to the risk of cytokine release induced hypotension).

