6.3 Missed Doses

For the planned analyses, patients within targeted blood pressure ranges (or below target without the use of any antihypertensives) at least 80% of the time will be considered as part of the per-protocol analysis. All patients will be evaluated in the intention to treat analysis regardless of the blood pressure range achieved or number of doses of antihypertensives given as long as imaging to assess osteonecrosis is available.

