10.3 Monitoring

To monitor the safety of therapy intensification, we will monitor for the following targeted toxicities: acute kidney injury (CTCAE grade 3 or higher not resolving to grade 0-1 within 72 hours) and syncope resulting in any injury. We will count events occurring during glucocorticoid containing phases only.

The intensive BP control arm (experimental) will be closely monitored for adverse effects and clinically suboptimal efficacy. The monitoring rules are constructed according to the Binomial group sequential design. We shall suspend the trial and investigate if any threshold defined in the rules is crossed.

AE monitoring in the intensive treatment arm: Probabilities of suspending trial to monitor > 25% targeted AE:

	True targeted AE probability			
	0.20	0.25	0.30	0.35
Suspend if number of AEs >7/20	0.03	0.07	0.23	0.40
Suspend if number of AEs >13/40	0.01	0.03	0.14	0.22
Suspend if number of AEs >25/80	0.00	0.01	0.12	0.18

Monitoring of missing the target in the intensive treatment arm: against <70% Probability of stopping

	True success probability			
	0.55	0.60	0.70	0.75
Suspend if number of successes <12/20	0.59	0.40	0.11	0.04
Suspend if number of successes <24/40	0.17	0.13	0.07	0.03
Suspend if number of failures <51/80	0.19	0.24	0.04	0.00

Efficacy monitoring of failures at reinduction II MRI (failure defined as $\geq 30\%$ involvement in any joint) against >50% failure rate.

	True success probability				
	0.35	0.40	0.45	0.50	0.55
Suspend if # successes <7/20	0.42	0.25	0.13	0.06	0.02
Suspend if # successes <16/40	0.31	0.23	0.13	0.05	0.01
Suspend if # successes <33/80	0.17	0.17	0.08	0.02	0.00

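### The 51/80 attainment row in 10.3 says failures where its printed probabilities fit successes, and the 78.7% power in 10.4 holds only at full target attainment

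*Combined protocol and SAP*

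**What the plan says.** **Monitoring (Section 10.3).** The attainment table is headed "Monitoring of missing the target in the intensive treatment arm: against <70% Probability of stopping". Its columns are true success probabilities of 0.55, 0.60, 0.70 and 0.75. The first two rows suspend the trial on too few successes (fewer than 12 of 20, fewer than 24 of 40). The third row reads "Suspend if number of failures <51/80". The section says the trial is suspended and investigated if any threshold is crossed. It does not say what makes a patient a success.

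**Power (Section 10.4).** The control arm is a mixture of above-target and within-target patients: "the distribution of the number of affected joints in the control group is anticipated to be $PC(k)=0.854*P_0(k)+0.146*P_1(k"). The intensive arm is not a mixture: "the distribution in the treatment group is anticipated to be $PT(k)=P_1(k"). From 0.385 against 0.20 the plan concludes that "the one-sided test has the exact power of 78.7% to detect the above anticipated difference at the 5% significance level". No other power is given.

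**Analysis set.** Section 10.4 states: "All randomized patients with appropriate imaging are considered evaluable and all analyses will be done according to intent-to-treat". Section 6.3 agrees: "All patients will be evaluated in the intention to treat analysis regardless of the blood pressure range achieved", provided imaging is available. It defines a separate per-protocol set based on being in range at least 80% of the time.

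**The concern.** The third attainment row is an operative threshold. As worded it points the wrong way: a trial with few failures, meaning good attainment, would be suspended. The row contradicts its own probabilities and the two rows above it.

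The power statement raises a different issue. Readers will take 78.7% as the power of the intent-to-treat comparison, which includes imaged patients who never reach the intensive target. The plan foresees such patients. It monitors for them, it defines a per-protocol subset that excludes them, and Section 4.1 says that in some circumstances, with pressure still outside the range, "further modifications can be delayed until a subsequent visit". If a null result follows imperfect attainment, a reader relying on 78.7% would treat it as stronger evidence against the hypothesis than the design supports.

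**Working it through.** **Part 1: the attainment table.** Inputs from Section 10.3: looks at 20, 40 and 80 patients; suspend at fewer than 12, 24 and 51 successes. For each true success rate p, the binomial count is carried forward from look to look and paths that have already crossed are removed. Each entry is the probability of first crossing at that look.

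| Row | p = 0.55 | 0.60 | 0.70 | 0.75 |
|---|---|---|---|---|
| <12/20, printed | 0.59 | 0.40 | 0.11 | 0.04 |
| <12/20, computed | 0.586 | 0.404 | 0.113 | 0.041 |
| <24/40, printed | 0.17 | 0.13 | 0.07 | 0.03 |
| <24/40, computed | 0.169 | 0.134 | 0.025 | 0.005 |
| 51/80, printed | 0.19 | 0.24 | 0.04 | 0.00 |
| 51/80 as successes <51 | 0.191 | 0.236 | 0.045 | 0.005 |
| 51/80 as failures <51 | 0.245 | 0.461 | 0.861 | 0.954 |

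The successes reading matches the printed third row to within rounding. The literal reading does not, and it suspends more often as attainment improves. Fewer than 51 failures in 80 means at least 30 successes. A trial that reaches this look already has at least 24 successes in its first 40 patients, so the literal rule suspends it with probability above 99.99% at every true rate from 0.55 to 0.90.

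The 24/40 row reproduces at 0.55 and 0.60 but not at 0.70 or 0.75.

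**Part 2: power.** Inputs from Section 10.4: 80 per arm; above-target risk P0 = 50/120 = 0.4167; within-target risk P1 = 4/20 = 0.20; control risk 0.854 × 0.4167 + 0.146 × 0.20 = 0.385; exact one-sided test at 5%.

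*The plan's own figure.* Enumerating both binomial counts with the one-sided Fisher rejection region gives 78.67%, which reproduces the stated 78.7%.

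*Extension.* Let a be the share of analysed intensive-arm patients with the within-target risk, and Q the risk among the rest:

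PT = a × P1 + (1 − a) × Q

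The control risk stays at 0.385. Neither a nor Q is in the plan; both are assumptions. Three choices of Q are shown:

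- no benefit: Q = P0 = 0.4167
- control-arm risk: Q = 0.385
- half the benefit kept: Q = (0.4167 + 0.20)/2 = 0.3083

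Example: at a = 0.80 with no benefit, PT = 0.80 × 0.20 + 0.20 × 0.4167 = 0.2433.

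| a | No benefit: PT, power | Control-arm risk: PT, power | Half benefit: PT, power |
|---|---|---|---|
| 100% | 0.200, 78.7% | 0.200, 78.7% | 0.200, 78.7% |
| 90% | 0.2217, 67.8% | 0.2185, 69.5% | 0.2108, 73.5% |
| 80% | 0.2433, 55.6% | 0.2370, 59.3% | 0.2217, 67.8% |
| 70% | 0.2650, 43.2% | 0.2555, 48.6% | 0.2325, 61.8% |

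If non-attainers keep 25% to 75% of the benefit, power is 70.7–76.1% at 90% attainment, 61.8–73.5% at 80% and 52.5–70.7% at 70%.

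**The case against.** **On power.** Section 10.4 states its assumption openly and claims power only for the difference it displays. A reader might infer that 78.7% is miscalculated; it is not. A reader might also infer that the true power is 43% to 68%. The documents do not support that. They give no expected attainment under the intervention. The only anchored level is 70%, and that is a monitoring threshold, not a forecast. Giving non-attainers the full above-target risk is the most pessimistic of the cases shown. That risk comes from a historical chart review, not from patients being titrated to a target. The delay in Section 4.1 applies only when pressure is both closer to target than before and within 10 mmHg of it, so such patients may well keep some benefit. None of the choices of Q has better support in the documents than the others.

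Replacement also helps in part. Under Section 10.1, patients who leave for reasons in 7.1 or 7.2 before osteonecrosis is observed or before the MRI are replaced, and those reasons include toxicity, refusal and, at discretion, persistent non-adherence. Missing the target is not itself such a reason, so imaged non-attainers remain.

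**On monitoring.** The column heading and the two rows above make the intent of the third row recoverable, so it would be too strong to say that the trial would in practice always be suspended at 80 patients. Nor is it a defect that the rule rarely stops a trial with 80% attainment: it is set against less than 70%. These points limit the consequence, but the threshold remains wrong as printed.

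The per-protocol set and the comparison of achieved pressures can reveal poor attainment afterwards. They do not alter what the stated power means.

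**Conclusion.** Both parts hold, with different force.

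The 51/80 row is an error: its wording contradicts its own probabilities, and the printed figures identify successes as the intended word. In the same table the 24/40 entries at 0.70 and 0.75 are too high (0.07 and 0.03 against 0.025 and 0.005), and success is undefined.

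The 78.7% is correct but conditional on full attainment among analysed patients. What is missing is a statement of that condition and of how power falls without it. In every case computed with less than full attainment and less than full benefit among non-attainers, power is below 78.7%. How far below depends on two quantities the plan does not supply: at 80% attainment it ranges from 55.6% (no benefit) to 67.8% (half the benefit). All figures also take the plan's P0, P1 and control risk as given. This is a gap in transparency, not proof that the trial is too small.

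**What to change.** In Section 10.3:

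- change failures to successes in the 51/80 attainment row;
- recompute the 24/40 row at 0.70 and 0.75;
- state what counts as a success, and whether it is the same within-target status as in the power model.

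In Section 10.4:

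- describe 78.7% as the power when every analysed intensive-arm patient has the within-target risk;
- add a sensitivity table using PT = a × P1 + (1 − a) × Q at a = 70%, 80%, 90% and 100%, for more than one choice of Q, with a and Q both labelled as assumptions.

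The cost is one corrected word, two table entries, one definition, one sentence and one small table. No patients are added, and sample size, alpha and test are unchanged. The only downside is that the stated power looks less favourable.

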10.0 STATISTICAL CONSIDERATIONS

10.1 Sample size and accrual

It is logistically realistic and statistically sound (see below) to randomize 160 patients (80/arm) to the intensive or the standard antihypertensive arms. Patients who are randomized but drop out due to reasons as defined in Sections 7.1 and 7.2 before ON is observed or before the reinduction 2 MRI, are considered as inevaluable for the primary endpoint, and should be replaced. Based on past experience, we anticipate ~60 eligible patients to be randomized annually. Conservatively postulating a 12% drop out rate, we need to randomize 180 patients altogether. We thus anticipate a full accrual within 3.5 years.

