10.2 Randomization

Open-label, stratified block randomization with block size of 4³⁹. Randomization will be stratified by site (SJCRH and other), gender, self-declared race/ancestry (White Non-Hispanic and other) and hypertension requiring >1 dose of medication before Day 4 (Yes/No).

Analyses for the primary and secondary objectives will not be stratified. If it is determined that certain important factors are not balanced between the two treatment arms, appropriate regression models (such as logistic or integer response models) will be applied. The power assessment below is based on an unstratified Chi-square test.

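### The exact primary test is not named; 78.7% matches the conditional (Fisher) version, and naming Boschloo's test would add about 4 points of power at 80 per arm within the same 5%

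*Combined protocol and SAP*

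**What the plan says.** Section 10.4 (Primary Objective) splits the primary analysis into two parts. In the first part, the arms are "compared by the exact one-sided Chi-square test comparing the probability of having at least 1 affected joint". The anticipated proportions with no affected joint and with one or more are given in a small table: "Control 0.615 0.385" and "Treatment 0.8 0.2". For 80 subjects per group, the section states that "the one-sided test has the exact power of 78.7% to detect the above anticipated difference at the 5% significance level", and names the software used.

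Section 10.1 gives the evaluable sample: "randomize 160 patients (80/arm) to the intensive or the standard antihypertensive arms". Section 10.2 says that the primary and secondary analyses will not be stratified, and adds: "The power assessment below is based on an unstratified Chi-square test".

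Neither section says whether the exact test conditions on the total number of events, and neither reports the type I error that the test actually attains.

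**The concern.** Exact test is not a unique description for a 2x2 table. The conditional version (Fisher) fixes the total number of events. That leaves few possible outcomes, so the attained error usually lies well below the nominal level. An unconditional version fixes only the two arm sizes and can use more of the allowed 5%. Both control the error, but they differ in power and can differ in their conclusion for tables near the boundary.

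Two things are at stake. If the planned test is the conditional one, the trial gives up power that it could have with the same patients and the same alpha. And in an open-label trial, the choice between valid readings of the test should be settled before outcome data are seen.

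**Working it through.** **Inputs.** All are from the plan: 80 evaluable patients per arm (10.1); one-sided 5% (10.4); treatment rate 0.20 (10.4); control rate 0.385 (10.4). The control rate follows from the mixture in 10.4, with 50 of 120 above-target patients and 4 of 20 within-target patients having at least one affected joint: 0.854 × 50/120 + 0.146 × 4/20 = 0.3558 + 0.0292 = 0.385.

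**Method.** Let X be the control events and Y the treatment events. List all 81 × 81 outcomes (x, y), and mark those in the rejection region R. Then:

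- power = Σ over R of Bin(x; 80, 0.385) × Bin(y; 80, 0.20);
- true size = the maximum over a common rate p of Σ over R of Bin(x; 80, p) × Bin(y; 80, p), searched in steps of 0.0005.

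Fisher's test rejects when the hypergeometric tail probability P(Y ≤ y | x + y) is at most 0.05. With fixed margins in a 2x2 table, this is also the conditional exact one-sided chi-square test. Boschloo's test uses the same tail probability as its statistic, and raises the cut-off as far as the true size allows without exceeding 5%. At 80 per arm the cut-off is 0.0665.

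**Reproducing 78.7%, and the alternatives (80 per arm).**

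| Test, one-sided 5% | Power | Maximum true size |
|---|---|---|
| Fisher (conditional exact) | 78.66% | 3.64% (p about 0.33) |
| Chi-square with continuity correction | 78.2% | 3.6% |
| Unconditional exact, pooled-Z ordering | 82.5% | 4.83% |
| Boschloo (unconditional exact) | 82.8% | 4.94% |
| Uncorrected asymptotic chi-square | 83.2% | 6.2% (only at p near 0.035 or 0.965) |

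Of these, only Fisher's test rounds to the stated 78.7%. Its size at p = 0.20, 0.2925, 0.385 and 0.50 is 3.45%, 3.56%, 3.42% and 3.43%, so the unused error is not confined to unusual event rates.

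**Comparing rejection regions.** Boschloo's region contains every table in Fisher's region, plus 60 more. For example, with 31/80 control events, Fisher's test rejects at 20 treatment events (p = 0.045) but not at 21 (p = 0.064). Boschloo's test rejects at 21 as well, because 0.064 is below 0.0665.

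**Gain at 80 per arm:** 82.77 − 78.66 = 4.1 points.

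**Other evaluable numbers (control/treatment), same rates.**

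| Split | Fisher | Boschloo | Gain (points) |
|---|---|---|---|
| 78/78 | 77.4% | 81.7% | 4.3 |
| 80/78 | 77.7% | 82.2% | 4.5 |
| 78/82 | 77.8% | 82.0% | 4.2 |
| 82/78 | 78.2% | 81.1% | 2.9 |
| 77/83 | 79.2% | 82.1% | 2.9 |
| 82/82 | 79.4% | 81.8% | 2.3 |
| 84/84 | 80.7% | 82.8% | 2.1 |
| 90/90 | 82.9% | 85.7% | 2.7 |

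The cut-off for Boschloo's test was recomputed for each split. The gain is positive throughout and runs from about 2 to 4.5 points.

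**The case against.** The strongest reply is that nothing in the plan is wrong. It names an exact one-sided test, the alpha, the rates, the sample size and the software, and its power figure reproduces. Fisher's test controls the error, and conditioning on the margins is a legitimate position: given the observed total of events, 5% is the bound that matters. All of this stands. It makes the point one of efficiency and specification.

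It is also fair to say that the gain is small beside the uncertainty in the design rates. The 20% treatment rate rests on 4 of 20 patients. If the true treatment rate were 25%, power would be 51.8% with Fisher's test and 57.5% with Boschloo's. The gain remains, but it would not rescue the design.

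Three stronger readings are tempting and are not supported:

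- A reader might infer that 10.2 and 10.4 specify different tests. The sentence in 10.2 follows remarks on stratified randomisation and unstratified analysis. It reads as a general description of the test set out in 10.4, where the word exact is supplied. The two are compatible.
- A reader might infer that power is below 80% only because of the test. Sample size matters too, since Fisher's test reaches 80.7% at 84 per arm. The documents also state no 80% target.
- A reader might take the 6.2% size of the uncorrected asymptotic chi-square as a hazard for this trial. It arises only at event rates near 3.5% or 96.5%. For rates of 15% to 50% the maximum is about 5.1%, and 10.4 plans an exact test in any case.

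**Conclusion.** The point holds as a low-cost improvement. Section 10.4 leaves the type of exact test open, and the stated power fits the conditional version, whose true one-sided error at 80 per arm is at most about 3.6%. Boschloo's test keeps the error within 5%, loses no rejection that Fisher's test would make, and raises power from 78.7% to 82.8% at 80 versus 80. Across the evaluable splits checked, the gain is roughly 2 to 4.5 points.

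The conclusion rests on three assumptions. That the planned test is conditional is inferred from the numerical match, since the documents do not name it. The 3.6% is the error over repeated samples in which the total number of events varies. And the power figures take the plan's rates of 38.5% and 20% as given. The 78.7% is correct for the test that it matches and should not be described as a miscalculation.

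**What to change.** If the unadjusted 2x2 comparison stays primary, make these changes before outcome data are seen:

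1. In 10.4, name Boschloo's one-sided unconditional exact test at 5% as the test for the first part of the primary analysis. State that its p-value is computed for the evaluable numbers actually obtained in each arm.
2. Restate the power as about 82.8% at 80 per arm for 38.5% versus 20%, and note that the figure shifts with the final split.
3. In 10.2, add the name of the exact test to the sentence on the power assessment, for consistency.
4. Report Fisher's one-sided exact test as a sensitivity analysis.

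The cost is a change of wording, with no more patients, no added visits and no change in alpha. The one downside is that some readers prefer conditional inference, and the sensitivity analysis serves them. If the sponsor prefers to keep the conditional test, 10.4 should say so by name, and 78.7% can stand.
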